11.3 Procedures for Recording Adverse Events

All adverse events (including ADEs) and device deficiencies occurring during the course of the study will be recorded on the CRF whether or not attributed to the trial device. The information recorded will include but not be limited to:

- A description of the event
- The dates of the onset and resolution
- Action taken
- Outcome
- Assessment of relatedness to the device
- Whether the AE is serious or not
- Whether the AE arises from device deficiency
- Whether the AE arises from user error

The severity of events will be assessed on the following scale: 1 = mild, 2 = moderate, 3 = severe.

AEs/ADEs considered related to the device as judged by a medically qualified investigator or the Sponsor will be followed either until resolution, or the event is considered stable.

It will be left to the Investigator's clinical judgment to decide whether or not an AE/ADE is of sufficient severity to require the participant's removal from treatment. A participant may also voluntarily withdraw from treatment due to what he or she perceives as an intolerable AE/ADE. If either of these occurs, the participant must undergo an end of trial assessment and be given appropriate care under medical supervision until symptoms cease, or the condition becomes stable.

11.4 Reporting Procedures for Serious Adverse Events

Reporting of all Serious Adverse Events will be done in accordance with the European Commission Guidelines on Medical Devices Serious Adverse Event Reporting (MEDDEV 2.7/3; December 2010).

SAEs/SADEs that pose an immediate risk to patient health or safety, will be reported to the trial DSMC/Sponsor immediately or no later than 24 hours after the Investigator is aware and to the device manufacturer, competent authority and the REC within 2 calendar days of the Chief Investigator becoming aware of the event.

All other reported SAEs/SADEs will be reported to the trial DSMC and Sponsor competent authority within 7 calendar days of notification, if appropriate. This will not include SAEs that may be expected as part of the risks of routine care. Adverse device events (SADEs, USADEs) and device deficiencies will also be reported to the device manufacturer. All SAEs will be followed up to resolution.

SAEs/SADEs will be recorded for a time period going from verbal assent/PICSO device adoption to 30 days following the use of the device.

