10.2 Device Safety

PICSO treatment is safe. Potential complications associated to PICSO may include:

- a) Bleeding due to damage to the coronary sinus where the PICSO catheter is placed
- b) Bleeding in the groin from the femoral vein access.
- c) Long term blockage of the coronary sinus where the PICSO catheter sits.
- d) Helium leak from the catheter into the blood. A leak of helium into the patient could occur with a balloon rupture or hole. However the risk is significantly mitigated since the system can automatically detect any leakage and stop the procedure. The maximum helium volume that could enter the patient using the PICSO system is less than 10 ml. This volume is approximately 1/3 of the volume that could leak from a bursting intra-aortic balloon pump (IABP) catheter, that are used in routine clinical practice in the aorta (i.e arterial circulation), whereas the PICSO catheter is used exclusively in the venous

circulation.. A helium leak from the PICSO system is therefore regarded to constitute a low risk to the patient.

Data about PICSO are continuously increasing and in the two main studies performed in man so far (PREPARE-PICSO and PREPARE-RAMSES) only one procedure adverse event (tamponade secondary to coronary sinus perforation) has been described. This rate (<3%) of complication is further lower than that associated to the routine elective electrophysiological procedures to the coronary sinus in the context of tachycardia ablation or cardiac resynchronization therapy.

It is possible that the PICSO balloon may be dislodged from the coronary sinus into the right atrium. This event has no known safety implications for the patients, but it may affect the efficacy of the PICSO treatment. The PICSO console will detect the occurrence of such event and alert the clinical team. In such a scenario balloon repositioning will only be considered if the treatment time-interval is less than 60 minutes. In order to minimize the risk for the patient, repositioning will be performed under fluoroscopic guidance in the catheterization laboratory. Once the balloon is repositioned, the PICSO treatment will be continued to achieve a minimum total treatment time of 60 minutes to a maximum of 90 minutes from the time of stent deployment.

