11.6 Safety Monitoring Committee

The Oxford University Hospitals Trust will conduct a review of all SAEs/SADEs for the trial reported during the quarter and cumulatively. The aims of this committee include:

- To pick up any trends, such as increases in un/expected events, and take appropriate action
- To seek additional advice or information from investigators where required
- To evaluate the risk of the trial continuing and take appropriate action where necessary

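### Section 11.4 leaves routine-care SAEs out of the 7-day reports and section 11.6 reviews only reported SAEs, so an excess of routine-looking events would not be routinely visible to the safety committee

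*Combined protocol and SAP*

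**What the plan says.** Section 11.3 is inclusive. All adverse events and device deficiencies "occurring during the course of the study will be recorded on the CRF whether or not attributed to the trial device", with seriousness and relatedness to the device noted for each.

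Section 11.4 has two onward routes.

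- **Immediate risk.** "SAEs/SADEs that pose an immediate risk to patient health or safety, will be reported to the trial DSMC/Sponsor immediately or no later than 24 hours". No exclusion is attached to this route.
- **Everything else.** "All other reported SAEs/SADEs will be reported to the trial DSMC and Sponsor competent authority within 7 calendar days of notification, if appropriate". The next sentence is the exclusion: "This will not include SAEs that may be expected as part of the risks of routine care".

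Section 11.5 ties expectedness to the manufacturer's risk analysis. Neither it nor 11.4 lists the SAEs that count as expected from routine care.

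Under section 11.6 the Trust "will conduct a review of all SAEs/SADEs for the trial reported during the quarter and cumulatively". Its aims include "To pick up any trends, such as increases in un/expected events, and take appropriate action" and "To seek additional advice or information from investigators where required".

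Section 10.2 lists among the potential PICSO complications: "Bleeding in the groin from the femoral vein access".

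**The concern.** The committee's input appears narrower than its task. It is asked to notice increases in expected as well as unexpected events, but one class of expected event is filtered out upstream. The filter is applied case by case, without a pre-specified list.

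The class matters because harm from the device or the research procedures can look like ordinary PCI harm. Femoral vein bleeding is a listed PICSO risk, and access-site bleeding is also a familiar complication of catheterisation. The repeat catheterisation at 24-48 hours is described in section 11.9 as outside routine practice, yet its complications would resemble those of any catheterisation. When events like these are judged one by one, each may reasonably be called unrelated. Only a count would show that there are too many.

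The controls are historical OxAMI patients matched by propensity score (sections 10.1 and 12.2), so no concurrent randomised arm would expose an excess. The version history also records that the device's regulatory status was changed to non-CE-marked and that enrolment was later widened to all culprit locations. Both changes add to the value of complete aggregate safety data.

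**Working it through.** **1. What reaches the committee.** The plan states no figure on this point, so the main check is to follow each kind of SAE through sections 11.3 to 11.6.

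| Kind of SAE | On CRF (11.3) | Sent on under 11.4 | In the 11.6 review, plain reading |
|---|---|---|---|
| Immediate risk, expected or not | Yes | Yes, within 24 hours | Yes |
| Non-immediate, judged device-related (SADE) | Yes | Yes, within 7 days | Yes |
| Non-immediate, not judged device-related, not expected from routine care | Yes | Yes, within 7 days | Yes |
| Non-immediate, not judged device-related, expected from routine care | Yes | No | No |

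The gap is the last row only. No section sends the committee a listing or count of SAEs that were recorded on the CRF but not sent on.

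**2. How an event falls into the last row.** The exclusion depends on whether an event may be expected, not on what caused it. A SADE is an event attributed wholly or partly to the device (section 11.1). A groin bleed may fit both descriptions, and no rule says which then prevails.

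**3. Effect on a count (illustration).** Take n = 25, the number of treated and followed participants at which recruitment stops (section 8.4). The number treated could be larger. One event is 1/25 = 4%. Suppose, purely for illustration, that two events are classed as routine and left out. The exact two-sided 95% upper limits are:

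- 0/25 seen: 1 − 0.025^(1/25) = 13.7%.
- 2/25 seen (8%): the 0.975 quantile of Beta(3, 23) = 26.0%.

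**4. What full counts could detect (illustration).** The documents give no background rate and no alert threshold, so both are assumed. Background rates p0 are 5%, 10% and 20%. The flag r is the smallest count with P(X ≥ r | 25, p0) ≤ 0.05, where X is binomial. The chance of a flag is then P(X ≥ r | 25, 2·p0) for a doubling and P(X ≥ r | 25, 3·p0) for a tripling.

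| Assumed p0 | Flag at r or more | P(flag) with no excess | P(flag), doubled | P(flag), tripled |
|---|---|---|---|---|
| 5% | 4 | 3.4% | 24% | 53% |
| 10% | 6 | 3.3% | 38% | 81% |
| 20% | 9 | 4.7% | 73% | 99.6% |

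These chances apply when every event is counted. Events in the excluded class add nothing to the count the committee sees.

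**The case against.** The strongest reply is that the exclusion is an ordinary exemption from expedited reporting.

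- **Scope.** The sentence qualifies only the 7-day route. Section 11.4 also uses the word reported for an earlier step, since it speaks of reported events that will be reported. In 11.6 the word could therefore mean notified by the investigator, before any exclusion. That reading is possible, but the text does not settle it, and no section says that the committee sees the wider set.
- **Which body.** The exclusion concerns reports to the DSMC and competent authority, whereas the 11.6 review belongs to the Trust. The documents do not say whether these are one body. This limits how firmly the gap can be asserted, and it is itself a reason to clarify.
- **Which meaning of expected.** If 11.6 follows 11.5, the events to trend are those expected of the device, and leaving out routine-care events would not touch them. This too is open.
- **Device harm stays in.** The exclusion names SAEs, not SADEs, and the causality category for possible relation in section 11.2 is broad. This stands for events recognised as device-related. It does not help with events judged unrelated one at a time.
- **The groin example.** Section 11.10 says a femoral venous sheath is not placed routinely in all PCI. It also says one is used whenever further venous access is clinically needed. The example is arguable and shows a risk of misclassification, no more.
- **Other safeguards.** The CRF holds every event, the committee may ask for information, coronary sinus complications are an endpoint, and non-PICSO participants are enrolled concurrently. All of this stands. But a right to ask helps only once someone suspects a problem, and the coronary sinus endpoint does not cover access-site or catheterisation events.

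A reader might infer that these SAEs are withheld from the committee altogether, or that a device-driven excess could never be seen. For the reasons above, the documents do not support either inference.

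**Conclusion.** The point holds in limited form. On the plain reading of sections 11.4 and 11.6, non-immediate SAEs regarded as expected from routine care, and not judged device-related, are absent from what the committee regularly reviews, although its aims include spotting increases in expected events. An excess of such events would not be routinely visible to it.

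This rests on two assumptions that the documents leave open: that the DSMC of 11.4 supplies, or is, the committee of 11.6, and that reported in 11.6 means sent on under 11.4. If either is wrong, the remaining fault is unclear drafting.

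The size cannot be fixed from the documents. The two events in 25 are an illustration and do not show that any event would be misclassified or any committee decision changed. With about 25 treated patients, even complete counts would miss many doublings at low background rates: at an assumed 5%, about three in four (100% − 24% = 76%). The change makes detection possible, not assured. It is still worth making, because the design has no randomised comparator and the data are already collected.

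**What to change.** 1. **Section 11.4.** State that the routine-care exclusion applies only to the 7-day individual report, and list the SAEs it covers. State that an event meeting both the routine-care description and the SADE definition is reported as a SADE.
2. **Section 11.6.** State that the committee receives a quarterly and cumulative table of all CRF-recorded SAEs, including those expected from routine care, split by PICSO attempted or not. The split is descriptive. Non-PICSO participants mostly have IMR of 40 or below, and only PICSO recipients have the repeat catheterisation, so they are not a control group. The 30-day window in 11.4 runs from use of the device, so the table also needs a stated window for participants who had none.
3. **Sections 11.4, 11.5 and 11.6.** Reconcile them on whether the DSMC and the Trust committee are the same body, and on whether expected refers to the device or to routine care.

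The cost is a few sentences in an amendment and one table per quarter. Section 11.3 already records seriousness and relatedness, so no new data are needed and no treatment or clinical rule changes. If the sponsor meant only an exemption from expedited reporting, the first sentence of item 1 and the table in item 2 make that explicit.

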11.5 Expectedness

Expectedness will be determined according to the Manufacturers risk analysis report

11.6 Safety Monitoring Committee

The Oxford University Hospitals Trust will conduct a review of all SAEs/SADEs for the trial reported during the quarter and cumulatively. The aims of this committee include:

- To pick up any trends, such as increases in un/expected events, and take appropriate action
- To seek additional advice or information from investigators where required
- To evaluate the risk of the trial continuing and take appropriate action where necessary

11.7 Safety for PICSO

See 10.2

11.8 Safety for CMR

CMR is a safe and non-invasive technique with no known risk when appropriately supervised. It does not involve ionising radiation. Potential participants with ferromagnetic objects in their bodies or with implanted devices which can be damaged by the CMR magnet will be excluded. All participants entering the scanner room are screened for such objects. Gadolinium contrast is widely used for clinical indications in CMR and is safe. Occasionally it may cause a mild headache, nausea, itching and very rarely (< 1 in 1000) a more severe allergic reaction. It is cleared within hours by the body. Gadolinium has recently been associated with nephrogenic systemic fibrosis in patients with severe renal dysfunction; hence, as per departmental guidelines based on Food and Drug Administration guidelines, all patients with glomerular filtration rate (GFR) < 30 ml/min (stage 3-5 renal disease) should not be given gadolinium. Participants for whom there is a possible history of metal in the eye and we are unable to find documented clinical evidence that the metal has been removed, will be offered an orbital (eye) x-ray prior to their cardiac CMR scan to confirm or negate presence of metal in the eye. This will add 0.1 mSv additional radiation exposure; this is 1/260 of that incurred during a standard coronary angiogram procedure. There are no contraindications to short periods of supplementary oxygen in appropriately selected patients.

11.9 Safety of cardiac physiological measurements

Coronary pressure wire studies are routinely performed during PCI procedures. The repeat catheterizations 24-48 hours after PCI are not part of routine practice and special attention will be paid to minimize radiation and use of contrast agent. The risk of repeating cardiac catheterization is low; a commonly occurring consequence is bruising at the site of vascular access which can be treated with simple analgesia. Based on local audit data, the average radiation exposure for a patient during routine angiography is 5 mSv. The additional IMR measurement adds on average only 1.6 mSv to the procedure. The follow up visits for IMR measurement also allows a valuable clinical opportunity to assess the result of initial PCI, which not otherwise be performed.

11.10 Safety of blood sampling

Blood sampling performed during the procedure will be performed through either the femoral venous sheath, coronary sinus catheter or coronary artery catheter. The femoral artery sheath and coronary artery catheter are required for and routinely used for PCI to be carried out. Some discomfort and possible complications are associated with placement of the femoral arterial sheath, but this is already clinically indicated as a necessary part of the PCI. The femoral venous sheath is not routinely placed for all PCI procedures, but is used whenever additional venous access during PCI is required clinically, for example to place catheters in to the venous system, or catheters or pacing electrodes in to the right side of the heart, or infusion of drugs during the PCI procedure. Potential risks and complications associated with venous sheath placement are much less than arterial sheath placement, because blood is not under arterial pressure and because other potential risks are intrinsically lower in the venous circulation. Placement of a coronary sinus catheter is not routinely used during PCI, but is used routinely during other commonly performed cardiac interventions. The risk of additional complications is very low. The average volume of blood samples for research analyses taken at each sampling point would not exceed 40 ml.

12 STATISTICS

12.1 Number of Participants

The OxAMI-PICSO study aims to investigate the potential benefit of PICSO in a highly selected population of STEMI patients. In line with the data reported by Sayeed et al in a previous metanalysis on 7 studies about PICSO application in animal models, the recently published Prepare-RAMSES study also observed a 30% reduction in IS in the treatment arm, however such reduction was not statistically significant in comparison to the control arm [19]. The study, however could still show a benefit of PICSO in terms of IS reduction at six months follow up in the subgroup of patients receiving high PICSO quantity. The study, however, was significantly hampered by the inclusion of relative low risk patients and by a small sample size. The author managed indeed to deliver full PICSO treatment only in 63% of the initial planned cohort (12 patients, of the 30 planned, received a prolonged treatment with PICSO) [22].

In order to address the first limitation of the Prepare-RAMSES study, OxAMI-PICSO study will select patients with a preexisting higher IMR. In this way PICSO is meant to be applied only in a population at higher risk and highly likely to get benefit from its application.

In this regard assuming that the stricter inclusion criteria may allow to detect a substantial benefit from PICSO compared to the control group and expecting that this will allow to achieve a significant 29% reduction in IS as shown in Sayeed's metanalysis [19], we initially calculated a final sample size of 12 patients with complete final data per each group with an interval of confidence at 95% and a 80% power. However considering that this was the final same sample size enrolled in the Prepare-RAMSES study, initially meant to recruit 30 patients per arm, we propose to double the actual sample size from 12 to 25 per arm.

Allowing for participants who do not wish to undergo repeat cardiac catheterisation, or cardiac MRI, we anticipate that approximately 75 patients may be recruited to the study in order to achieve full participation and complete follow up in 25 subjects.

12.2 Analysis of Endpoints

In keeping with our usual practice we will obtain expert statistical advice from the Centre for Statistics in Medicine (or equivalent) for each specific task. Summary statistics, including means, medians, and

variances, will be calculated at each time point and for each type of data (e.g. parameters derived from coronary physiology and CMR). The distribution of the levels will be described. It may be necessary to log transform the data before further statistical analysis. For each parameter an analysis of variance will be carried out at each time point.

Control group in OxAMI-PICSO study is represented by a highly matched group of patients underwent to primary PCI, with a prestenosing IMR > 40 and with available 24 hours recath and 24-48 hours/6 months CMR data. Matching will be performed by application of a propensity score matching analysis including the following predictors in the model: age, sex, pain to wire time, thrombotic burden (assessed as angiographic thrombus score), thrombus aspiration performance, stent volume, glycoprotein IIbIIIa inhibitors adoption.

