4.3 Study Hypothesis

The Oxford Acute Myocardial Infarction - Pressure-controlled Intermittent Coronary Sinus Occlusion in STEMI (OxAMI-PICSO) study aims to analyze the potential benefit of PICSO in a selected population of STEMI patients. In patients with pre-stenting high IMR, and thus with larger infarct size and more compromised microvasculature status, PICSO treatment added to the conventional revascularization gold standard is expected to be associated to a better myocardial reperfusion. This will be assessed by measurement of indexes of coronary physiology and by CMR evaluation of indexes associated to infarct size, myocardial salvage and microvascular obstruction, and other biomarkers. The comparator group will be matched participants previously enrolled in the OxAMI study, with STEMI and with a pre-stenting IMR above 40.

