5. OBJECTIVES AND OUTCOME MEASURES/ENDPOINTS

Objectives	Outcome Measures/Endpoints
------------	----------------------------

Primary Objective
 
To assess the impact of PICSO on coronary physiology parameters, on infarct size, on myocardial salvage and on microvascular obstruction at CMR in a selected population of STEMI patients at higher risk of no reflow and with the theoretical prerequisites that make more likely to respond to PICSO treatment. The control group will be represented by a highly matched group of patients from the ongoing Ox-AMI (Oxford Acute Myocardial Infarction) project (Ethics Ref 11/SC/0397), who have undergone all other aspects of the study protocol, including assessment of coronary physiology at 24 hours post primary PCI, 24-48 hours and 6 months CMR, but who have not received PICSO treatment.
	
Area at risk, Infarct size, Myocardial salvage and microvascular obstruction measured by cardiac magnetic resonance at 24-48 hours

Secondary Objectives
 
The OxAMI-PICSO study aims to evaluate the utility of individual biomarkers (blood components derived substances from cells, DNA, plasma etc) in the assessment of coronary artery disease and myocardial infarction. The OxAMI-PICSO may show also how these individual biomarkers may be modified by PICSO treatment.
	
Coronary flow reserve (CFR), Fractional Flow reserve (FFR), index of microcirculatory resistance (IMR) measured at 24 hours after PCI.
 
Infarct size and microvascular obstruction extent measured by cardiac magnetic resonance at 6 months
 
Individual Biomarkers related to coronary artery disease/myocardial infarction at three time points (PCI, 24/48 hours after PCI and 6 months). These include: blood biomarkers of myocardial injury, metabolism and inflammation.

Tertiary Objectives
 
To evaluate the rate of PICSO failure deployment, coronary sinus complications, and additional time and radiation exposure associated to for PICSO deployment
	
Rate of PICSO failure deployment
 
Rate of coronary sinus complications: perforation, dissection, thrombosis
 
Time for PICSO deployment / additional screening time and radiation dose

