7.2. Inclusion Criteria

Participants must satisfy the following conditions:

- Male or Female, aged 30 to 90 years,
- Clinical presentation with STEMI
- Referred for coronary angiography with view to proceed to PCI with stenting.

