9.4 Analysis of cardiac physiological measurements

Cardiac and/or coronary flow and pressures will be measured, before and after stenting and during the repeat coronary angiogram at 24 hours post-PPCI, using commercially available measurement guidewires

according to standard techniques that are in routine use in current PCI practice. The guidewire contains a pressure-temperature sensor to allow for calculation of the physiological parameters. The guide wire is calibrated at the beginning of the PCI and then advanced into the distal third of the culprit artery. Calculations will be based on measurements of proximal and distal coronary pressure(s) and mean transit time (in seconds) during maximal hyperemia, as previously described. Briefly a pressure wire (Radi; St Jude Medical, St Paul, MN, USA) is placed in the LAD distal to the lesion. Baseline mean aortic pressure (Pa), mean distal pressure (Pd) and Pd/Pa ratio will be recorded. Thermodilution-based measurement of CFR and IMR will be performed by injecting in the IRA 5 ml of room temperature saline solution and recording mean transit time (meanTt) at baseline and after induction of maximal hyperaemia by intravenous infusion at a rate of at a rate of 140 mg/kg/min. Once hyperaemia is achieved the following parameters will be obtained: FFR (Pd/Pa during hyperemia), CFR (meanTtbaseline/meanTthyperaemia) and IMR (Pdhyperaemia* meanTthyperaemia).

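### Section 12.2 neither matches on nor adjusts for the pre-stenting IMR value above 40 or the culprit vessel; this matters most for IMR at 24 hours and should be handled by a prespecified adjusted model

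*Combined protocol and SAP*

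**What the plan says.** The controls are historical. Section 4.3 describes them as "matched participants previously enrolled in the OxAMI study, with STEMI and with a pre-stenting IMR above 40", and section 10.1 says that they are propensity-score matched patients from the OxAMI study.

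Section 12.2 requires controls "with a prestenosing IMR > 40 and with available 24 hours recath and 24-48 hours/6 months CMR data". The propensity model contains "age, sex, pain to wire time, thrombotic burden (assessed as angiographic thrombus score), thrombus aspiration performance, stent volume, glycoprotein IIbIIIa inhibitors adoption". The analysis is then "For each parameter an analysis of variance will be carried out at each time point". No covariate, balance check, matching ratio or adjusted analysis is given there or elsewhere.

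Section 5 lists among the secondary outcomes the "index of microcirculatory resistance (IMR) measured at 24 hours after PCI". Section 9.4 says that coronary physiology is measured "before and after stenting and during the repeat coronary angiogram at 24 hours post-PPCI", so each PICSO patient has a pre-stenting value of the same quantity.

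On culprit vessel, the inclusion criteria in section 7.2 ask only for "Clinical presentation with STEMI" and referral for PCI, with no limit on location. The version table in the synopsis records that version 5.0 widened enrolment to any culprit location. Sections 4.3 and 12.2 state no culprit rule for controls.

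**The concern.** With no randomisation, the matching list and the analysis model are the main protection of the group comparison. Two pre-treatment variables appear in neither.

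*Pre-stenting IMR.* Both groups are restricted to values above 40, so high against low IMR is dealt with. The value above 40, for which section 6 sets no upper limit for PICSO, is not used. For 24-hour IMR it is the patient's own baseline. The preliminary OxAMI findings in section 4.1 say that the change in IMR across stenting depends on the starting value: little change when it is low, the largest fall when it is above 40, and some patients staying high or rising. The post-stenting value cannot take its place, because section 8.3 puts the start of PICSO before stenting.

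*Culprit vessel.* The version 5.0 entry implies that earlier PICSO patients were selected on location and later ones were not. With no stated rule for controls, a systematic imbalance is plausible.

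A systematic difference does not shrink as the sample grows. It could be read as a PICSO effect or could hide one. Chance imbalance is a different matter: the standard error already covers it.

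**Working it through.** The plan has no figure of its own on this point. Its initial 12 per group (section 12.1) cannot be reproduced, because no SD is given; it implies an effect of (1.96 + 0.84) × √(2/12) = 1.14 SD. Only the final 25 per arm is used below.

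**Inputs**

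| Input | Value | Source |
|---|---|---|
| Patients per arm | 25 | Section 12.1 |
| Outcome SD | 1 (all shifts in SD units) | Scaling |
| Systematic IMR imbalance after matching | 0.3 SD | Assumption |
| Whole-population correlation, IMR with infarct size | 0.3 to 0.5 | Assumption |
| Whole-population correlation, pre-stenting with 24-hour IMR | 0.7 | Assumption |
| Share of patients with IMR above 40 | top 30% to 50% of a normal distribution | Assumption |
| Culprit imbalance; infarct-size gap without PICSO | 20 points; 0.5 to 1.0 SD | Assumption |

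**Step 1: precision.** SE = √(2/25) = 0.283. The 95% half-width on 48 df is 2.011 × 0.283 = 0.569 SD.

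**Step 2: restriction to IMR above 40.** Selecting the top 30% or 50% leaves a fraction v = 0.265 or 0.363 of the IMR variance. The correlation within the selected group is r′ = r√v / √(1 − r² + r²v), and the shift is 0.3 × r′.

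| Whole-population r | r′ (top 30% / 50%) | Shift, SD |
|---|---|---|
| 0.3 | 0.160 / 0.186 | 0.048 / 0.056 |
| 0.5 | 0.285 / 0.329 | 0.085 / 0.099 |
| 0.7 | 0.450 / 0.509 | 0.135 / 0.153 |

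**Step 3: culprit vessel.** Shift = 0.20 × 0.5 = 0.10 SD, up to 0.20 × 1.0 = 0.20 SD.

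**Step 4: rejection rate of the two-sided 5% test with no PICSO effect** (noncentral t, 48 df, noncentrality = shift / 0.283).

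| Contrast | Shift, SD | Share of half-width | Rejection rate |
|---|---|---|---|
| Infarct size, IMR | about 0.05 to 0.10 | 9% to 18% | 5.3% to 6.4% |
| 24-hour IMR, own baseline | 0.135 to 0.153 | 24% to 27% | 7.5% to 8.3% |
| Infarct size, culprit vessel | 0.10 to 0.20 | 18% to 35% | 6.4% to 10.7% |

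**Step 5: effect of adjusting.** Studies were simulated with no PICSO effect, an imbalance in IMR (r = 0.3 or 0.5 within the selected group) or in culprit vessel (70% against 50%), and a linear outcome model. Including the covariate returned the rejection rate to 4.9% to 5.0%. This follows by construction, since the fitted model matches the generating one. It shows that the measured part of the bias is removable, not that the model would be right in practice.

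**Step 6: power at an assumed 0.70 SD effect.** Unadjusted, 48 df: 67.9%. If the covariates predict nothing and errors are clustered on 25 pairs (about 24 df): 66.1%. If r = 0.3: 71.9% on 46 df, 70.2% on 24 df. Precision is not the argument for adjusting.

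**The case against.** The case for leaving the plan alone has four parts.

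- *Both groups already have IMR above 40, and the documents describe no infarct-size gradient above that threshold.* This stands. It is why the IMR effect on infarct size is probably small. The preliminary findings in section 4.1 also concern change across stenting and give no slope above 40. The argument is weaker for 24-hour IMR, where the covariate is the endpoint's own baseline.
- *The documents do not say that culprit vessel predicts infarct size without PICSO.* This stands too. Section 4.2 links anterior location only to expected response to the device. The 0.5 to 1.0 SD gap is purely an assumption, and a main-effect term would not deal with a difference in response.
- *Matching on seven variables may balance the other two, and section 12.2 promises expert statistical advice.* Matching would remove only the part correlated with the listed variables, and no balance check would show what is left. The advice leaves room for adjustment but does not prespecify it.
- *Area at risk and myocardial salvage, listed in section 5, would help to interpret a difference in territory.* They might reveal one; they do not correct the infarct-size or 24-hour IMR contrast.

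A reader might also take the statement in section 9.4 that the wire "is placed in the LAD distal to the lesion" as evidence that the PICSO group is all or mostly LAD. It is not. The same section also places the wire in the culprit artery, without limiting which one. This is a separate inconsistency with the eligibility criteria, to be reconciled there, and it says nothing about imbalance against controls.

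**Conclusion.** The omission is real and worth correcting, with a modest expected effect. Neither the matching nor the model uses the pre-stenting IMR value or the culprit vessel.

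The point is strongest for 24-hour IMR, at about 7.5% to 8.3% rejection for a nominal 5% under the stated assumptions. For infarct size, the IMR part is probably small (5.3% to 6.4%). The culprit part could be larger (6.4% to 10.7%), but only if a prognostic difference exists that the documents do not describe.

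A reader might infer that the comparison is biased in favour of PICSO, or that a positive infarct-size result could not be trusted. The documents do not support this: they give no SD, correlation, culprit split or balance data, and so show neither the size nor the direction of any bias. Using r = 0.7 for 24-hour IMR without the range restriction would give about 11%, but nothing in the documents supports exempting that correlation from the restriction applied to the others.

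**What to change.** In section 12.2, replace the unadjusted analysis of variance for the group comparison with a prespecified linear model in the matched set:

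- 24-hour IMR: group plus pre-stenting IMR.
- Infarct size: group plus pre-stenting IMR and culprit vessel (anterior against other).
- Use the same IMR scale in both models, for example log.
- If matching is 1:1, standard errors may be clustered on pair, with about 24 df.

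Report the adjusted difference with its 95% confidence interval, the standardised differences on both variables after matching, and the unadjusted matched comparison as supportive.

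Adding the two variables to the propensity model is optional and may cost matches. With 25 treated patients, the number per predictor falls from 25/7 = 3.6 to 25/9 = 2.8. The documents do not state the size of the control pool; the figure of about 250 in section 8.1.1.1 describes experience with assent and should not be read as that pool.

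The cost is a few sentences. Pre-stenting IMR is already required in controls. Culprit vessel should be readable from the angiogram needed for the thrombus score, which is an inference. Residual df fall from 48 to 47 (24-hour IMR) or 46 (infarct size). With pair clustering and covariates that predict nothing, power falls by about 2 points, as worked above.
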